1.0 General Information

***Please enter the full title of your study:**

Can Virtual Reality Reduce Patient's Pain, Improve Patient's Experience, and Reduce Procedure Related Anxiety with Venipuncture? A Randomized Control Trial.

***Please enter the Protocol Number you would like to use to reference the protocol:**

19-35

* This field allows you to enter an abbreviated version of the Protocol Title to quickly identify this protocol.

Is this a multi-site study (i.e. Each site has their own Principal Investigator)?

No

Does this protocol involve the use of animals?

Yes No

4.0 Project Information

4.1 * Has another IRB/HRPP reviewed this study or will another IRB/HRPP be reviewing this study? If Yes, answer the questions according to the IRB/HRPP Determination.

Yes No

IRB Name	Review Date	Determination
No records have been added		

4.2 * Is this a research study or a Compassionate Use/Emergency Use/HUD project?

Yes No

4.3 What type of research is this?

- Biomedical Research
- Clinical trial (FDA regulated)
- Behavioral Research
- Educational Research
- Psychosocial Research
- Oral History
- Other

Describe other:

Investigational research

8.1 Is this a collaborative or multi-site study? (e.g., are there any other institutions involved?)

Yes No

8.2 Study Facilities and Locations:

Institution	Site Name	Site Role	FWA or DoD Assurance Number	Assurance Expiration Date	Is there an agreement?	IRB Reviewing for Site	
No records have been added							

Other:

Other Institution Site	Site Role	FWA or DoD Assurance Number	FWA or DoD Expiration Date	Is there an agreement?	IRB Reviewing for Site	
No records have been added						

8.3 Are there international sites?

Attach international approval documents, if applicable, when prompted. Note: Ensure local research context has been considered

Yes No

8.4 Is this an OCONUS (Outside Continental United States) study?

Yes No

Select the area of responsibility:

Have you obtained permission from that area of responsibility? (This is a requirement prior to study approval)

Yes No

9.0 Study Details

9.1 Key Words:

Provide up to 5 key words that identify the broad topic(s) of your study

virtual reality, pain control, procedure related anxiety, distraction

9.2 Background and Significance:

Include a literature review that describes in detail the rationale for conducting the study. Include descriptions of any preliminary studies and findings that led to the development of the protocol. The background section should clearly support the choice of study variables and explain the basis for the research questions and/or study hypotheses. This section establishes the relevance of the study and explains the applicability of its findings

The use of distraction with media devices to assist in pain control has progressed in leaps and bounds in the last 15 years. Methods of distraction include, but are not limited to, video games, iPads, television, Augmented Reality, Virtual Reality (VR), cognitive behavioral therapy, and hypnosis. As reported by Mahrer and Gold, Virtual Reality has been studied with success in the treatment of burn patients undergoing physical therapy in multiple studies pitting VR against standard analgesia, video games, audio recordings, and cognitive behavioral therapy. Virtual Reality has also been successfully tested by Nilsson et al. in pediatric cancer patients receiving chemotherapy. They report a significant reduction in pain and distress during placement of subcutaneous venous port access. Furman et al. showed improved pain scores during dental procedures while watching movies. Additionally, there have been two studies on routine procedures by Gold et al. who investigated blood draws and intravenous placement of contrast for MRI scans in pediatric patients, both of which showed improved pain and anxiety scores. A recent randomized controlled trial by Özalp Gerçeker et al. showed reduced pain, fear and anxiety in pediatric patients undergoing blood draws when using VR devices, including a group which used the Ocean Rift application.

The technology relating specifically to Virtual Reality has seen significant changes in the last 5 years. Previously, Virtual Reality devices required either a direct connection to a local computer or even a dedicated system to run them. New to the market in the last few years are devices which do not require a connection to a computer, phone, or internet for some functions. This is significant as these devices can be used in any environment with minimal equipment. Additionally, Malloy and Milling report that the use of more sophisticated technology with improved immersion is associated with even greater relief of pain. Although there are alternative methods for anxiety and pain control in the emergency setting, the use of immersive virtual reality (virtual reality methods in which the user is able to interact with the virtual environment) with these new standalone devices may improve pain control and anxiety associated with procedures, decreasing the need to use anxiolytics, opioids, and anesthetics in the emergency department. If a significant difference is found between the standard practice of performing venipuncture without pain control or virtual reality and the standard practice with the addition of virtual reality, then there would be strong implications to utilize the method in the emergency department setting. This could lead to future studies on additional procedures

with VR such as laceration repair, nail trephination, digital blocks, nail removal, lumbar punctures, and incision and drainage of abscesses.

In order to support the hypothesis of this study, which is that there will be a clinically significant decrease in pain perception when patients use virtual reality devices during venipuncture, a literature review was conducted focusing on articles published from 2000 to present using key terms *virtual reality*, *pain control*, *distraction*, and *procedure related anxiety*. The review was conducted on databases such as Pubmed, Ovid, Cochrane, Medline, Google Scholar, and a hand search through references used in applicable articles. A total of 60 articles were reviewed for relevance. Of the 60 reviewed articles, 23 were selected for their relevance to the research question. The literature review shows no studies of note have been conducted which would be applicable to an adult population for similar procedures (ie. venipuncture).

Given the lack of research on the use of VR with common procedures such as IV access in an adult population, it remains unclear whether the use of VR would be beneficial in this population, or if the benefits are limited only to pediatric patients. If the results of this study show significant improved pain and anxiety levels in adults, thus rejecting the null hypothesis (which is that there will be no significant difference in pain or anxiety with and without the use of virtual reality), it would be reasonable to initiate further research into the use of VR for other common procedures performed in the emergency department, laboratory, family practice, or in the military setting while deployed.

9.3 Objectives/Specific Aims/Research Questions:

Describe the purpose and objective(s) of the study, specific aims, and/or research questions/hypotheses

The study's primary outcome is to determine if the use of immersive virtual reality with the Oculus Go improves the patient's pain ratings and pain intensity levels when undergoing venipuncture during routine blood draws versus the standard practice. We will use the Visual Analogue Scale (VAS) for pain assessment after each blood draw.

The study's secondary outcome is to assess procedure related anxiety before and after each intervention, which will also be measured with the VAS. We will also use the Likert scale to measure participant satisfaction with the procedure and whether or not they would request the use of VR again if available.

9.4 Study Design:

Describe study design in one to two sentences (e.g., prospective, use of existing records/data /specimens, observational, cross-sectional, interventional, randomized, placebo-controlled, cohort, etc.). Specify the phase – Phase I, II, III, or IV – for FDA-regulated investigational drug research

This study is a prospective randomized controlled trial comparing the standard practice for venipuncture to the standard practice with the addition of Virtual Reality. In order to test our hypothesis, we will be conducting this study in the phlebotomy lab on patients aged 18-50 years old who are already undergoing venipuncture for routine lab testing.

The study will test the participant's acute pain level associated with the procedure, as well as testing their level of procedure-related anxiety before and after the procedure.

9.5 Target Population:

Describe the population to whom the study findings will be generalized

Adults over the age of 18 who are undergoing venipuncture for routine purposes. We expect the results to be generalizable to the full Military population as well as Civilians of the same age with similar concerns about pain or anxiety related to the procedure.

9.6 Benefit to the DoD:

State how this study will impact or be of benefit to the Department of Defense

The use of distraction with media devices to assist in pain control could have significant benefit to the DoD, particularly in the acute pain setting, to include the emergency setting, and Soldiers in the deployed setting. In the emergency setting, the use of VR could significantly improve patients' overall

experience and satisfaction with their visit, as well as reducing their pain and anxiety associated with having minor procedures performed. As noted by Fields et al. having an IV started is the most painful procedure performed during many patients emergency department visit. Given an improved patient experience, the use of VR could improve overall patient satisfaction scores on post visit surveys as well. Separately, but of equal importance, the use of standalone, immersive virtual reality could significantly benefit Soldiers in the Deployed setting. In the deployed setting, supplies for patient care can be variably available, to include adequate amounts of medications such as anxiolytics, opioids, and anesthetics. This is also applicable to large-scale training events such as NTC or JRTC where supplies for pain control may be even scarcer. A single VR unit does not expire, is reusable, and can be purchased for less than \$200. If the results of this study show improved pain scores, it would be reasonable in a deployed/training environment setting to use the device as an adjunct to pain control and patient care in order to improve Soldiers treatment.

10.0

Study Procedures, Data Management, and Privacy

10.1 Study Procedures:

[figure not shown]
Describe step-by-step how the study will be conducted from beginning to end

A prospective randomized controlled trial comparing standard practice for conducting venipuncture to standard practice with the addition of Virtual Reality using the Oculus Go Head Mounted Display (HMD). The study will be performed on volunteers who are reporting to the phlebotomy lab to have venipuncture for blood draws that were previously ordered by their health care providers. Participants who were not already scheduled to undergo routine venipuncture will not be included.

[figure not shown]
When approaching the ticket stand to draw a waiting number for the lab, prospective participants will be asked by an assistant investigator located near the kiosk if they are interested in participating in the study. If the participants express interest, they will be directed to the screening station. The screening station will be set up in a private room near the lab waiting area, and participants will be screened for eligibility and educated on the benefits and risks of the study. They will also provide informed consent if they decide to participate.

All participants will be asked to fill out a self-reported data questionnaire in addition to the informed consent document to assess for inclusion and exclusion criteria discussed later in this protocol. This questionnaire will assess the participant's expected level of anxiety prior to the procedure and expected level of pain associated with the procedure by utilizing a visual analog scale (VAS). The VAS will be on a 100 millimeter line similar to the one shown below:

Expected level of **Anxiety** before having blood drawn

Expected level of **Pain** with needle insertion for blood draw

Once approved for participation in the study all participants will undergo a brief instructional class on how to operate the HMD and will be allowed sufficient time to become comfortable with its use. We expect approximately 5-10 minutes to be required for this portion of the study. Once familiar with the use of the VR headset, participants will be asked to randomly draw an envelope from a container. This envelope will contain a block and sequence number. The block and sequence number will be the subject ID and will correspond to a predetermined number set on a separate document that will determine if the participant will use the HMD during venipuncture or not. The screener will not have immediate access to the list showing which group the participant will be assigned to. One member of the study team will be present in the lab room to ensure the participant uses the VR headset (or not) according to what is randomly drawn. This member of the research team will have the list showing whether or not the participant is assigned to the control arm or the experimental arm. The participants will then proceed to the specimen room to undergo venipuncture.

Venipuncture for both groups will occur in the non-dominant arm. The reasoning for this is that the Oculus Go requires one free hand to use a controller. This will ensure that the individuals participating are able to effectively use the device. Those unable to undergo venipuncture in the non-

dominant arm will undergo venipuncture in the dominant arm instead and will use the Oculus Go controller with their non-dominant hand.

Those utilizing the Oculus Go HMD will be interacting with the VR game Ocean Rift. They will utilize a single controller to explore an underwater safari park. Ocean Rift has multiple environments to choose from, including coral reefs, ship wrecks, lagoons, the arctic, and prehistoric seas. Participants may interact with and learn about different creatures to include dolphins, turtles, orcas, ray, whales, sea lions, manatees, and dinosaurs. During the game users may travel where they please and interact with what they choose. The VR device is equipped with head-tracking software that allows the user to choose direction by looking around. The entire interior and exterior of the headset will be cleaned with alcohol-based wipes after each use. Alcohol will be used since it is generally well-tolerated on human skin, and since it evaporates quickly. The headset will be dried in the open air for a minimum of two minutes between each subject's use.

Those not using the VR will still wear a headset that will simply be turned off. This is to ensure that any significant change noted with the VR is due to the use of VR itself, and not simply due to "blindfolding" the patient during the procedure.

As some patients experiencing anxiety may be tempted to move during the procedure, lab personnel will instruct participants to remain still during venipuncture. Participants will be advised that they may take breaks as needed if anxiety becomes overwhelming.

After undergoing the procedure, each participant will be asked to fill out the post-procedure questionnaire and return it to the study team member present in the lab room, who will clean the headset as the participant completes the questionnaire. This questionnaire assesses the patient's pain intensity and level of anxiety with the VAS similar to the VAS shown above, as well as the patient's satisfaction with the visit which will be measured utilizing a Likert scale for individual questions (see below).

Overall, how satisfied were you with the use of Virtual Reality in reducing your pain level?

5 Very Satisfied	4 Satisfied	3 Not Sure	2 Unsatisfied	1 Very Unsatisfied
---------------------	----------------	---------------	------------------	-----------------------

Overall, how satisfied were you with the use of Virtual Reality in reducing your anxiety level?

5 Very Satisfied	4 Satisfied	3 Not Sure	2 Unsatisfied	1 Very Unsatisfied
---------------------	----------------	---------------	------------------	-----------------------

How likely would you be to request Virtual Reality if it were available for use for other painful or anxiety-inducing procedures?

5 Very Likely	4 Likely	3 Not Sure	2 Unlikely	1 Very Unlikely
------------------	-------------	---------------	---------------	--------------------

10.2 Data Collection:

Describe all the data variables, information to be collected, the source of the data, and how the data will be operationally measured.

The independent variable for this study is the use of VR or lack thereof. The dependent variables include accurately measuring anxiety levels pre and post procedure, pain levels after the procedure, and satisfaction with the procedure in regards to pain control, anxiety management, and ease of use. The participant's gender, age, and a minimal medical history will be obtained for purposes of inclusion or exclusion from the study. The information collected relevant to the conduct of the study will include any history of bloodborne disease, anxiety, seizures, pregnancy status, right vs left handedness, VR experience, nausea, vomiting, or vertigo. Participants will also be asked to rate their expected pain and anxiety associated with venipuncture using the Visual Analog Scale (VAS). The above information will be collected on the self-reported data sheet prior to providing specimens. The questionnaires will also enquire as to whether the participant took any pain medications prior to arrival, as well as rate pre and post-procedure anxiety level on a VAS scale. Finally, patients will then rate their procedure related pain intensity on the VAS scale.

Participants will also be asked about their satisfaction level with the use of VR in regards to pain control, anxiety management, and ease of use and their likelihood of requesting VR if available in the future using the Likert scale. All information will be provided and data collected voluntarily, and participants may choose not to answer any questions they choose.

The VAS will be measured using a 100 millimeter line on which the participant will be instructed to place a mark corresponding to their pain or anxiety, i.e. 5 would be very little anxiety and 95 would be very high anxiety. The data will then be acquired using a metric ruler and the corresponding number will be documented. The Likert scale will be measured using a one to five numeric scale on which the patient will be asked to rate their satisfaction with the use of the VR headset in regards to pain control, anxiety management, and ease of use, and their likelihood of requesting its use again, 1 being very unlikely, 2 likely, 3 unsure, 4 likely and 5 very likely.

10.3 At any point in the study, will you request, use, or access health information in any form, including verbal, hard copy and electronic?

Yes No

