13.0 Recruitment and Consent

13.1 Please describe the recruitment process, including how subjects will be identified and selected for the study.

When approaching the ticket stand to draw a waiting number for the lab, prospective participants will be asked by an assistant investigator located near the kiosk if they are interested in participating in the study. Participants will be selected in consecutive order (as long as the screening room is open) to avoid selection bias. However, patients who are obviously outside of the age range of 18-50 will not be asked to participate, although this process may leave room for some selection bias. If participants express desire, they will move to a screening station located in a private room near the lab to be educated on the details of the study, to include any risks. If they consent, they will fill out a screening questionnaire. If patients are eligible, they'll be given a brief tutorial on use of the VR headset and randomly assigned an envelope containing a card stating that they will use VR during venipuncture or undergo standard practice (the researcher will be blind to which group the participant is assigned to). Once instruction is complete, they'll return to the lab waiting area to draw a ticket to provide a specimen IAW standard lab practice.

13.2 Compensation for Participation:

There will not be any compensation (payment or otherwise) for participating in this study.

13.3 Please describe the pre-screening process. If no pre-screening, enter Not Applicable in the text editor

When patients approach the ticket kiosk, a member of the study team will ask them if they're interested in participating in a study related to pain control with venipuncture. To avoid perceived coercion, the recruiter will be in scrubs so that his rank will not be visible. If the participants wish to participate, they'll be directed to a screening station in a private room.

At the screening station, candidates will be screened to insure they meet inclusion/exclusion criteria by completing a prescreening form that addresses all participation criteria. After that, they'll be provided informed consent documents and will undergo a brief tutorial for use of the VR headset prior to returning to the lab waiting area to draw a ticket.

13.4 Consent Process:

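### The anxiety outcome pairs an expectation rated at screening with a post-draw rating that has no stated reference period, and the analysis text names only the pre-procedure score

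*Combined protocol and SAP*

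**What the plan says.** Section 9.3 sets the outcome: "The study's secondary outcome is to assess procedure related anxiety before and after each intervention", on a 100 mm VAS. The null hypothesis in section 9.2 covers anxiety as well as pain, with and without VR.

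Section 10.1 gives the steps. On the self-report form completed at screening, "This questionnaire will assess the participant's expected level of anxiety prior to the procedure and expected level of pain associated with the procedure". Next, "Once approved for participation in the study all participants will undergo a brief instructional class on how to operate the HMD", for which 5-10 minutes are allowed, and the participant then draws an envelope. Section 13.1 has the same order ("If patients are eligible, they'll be given a brief tutorial on use of the VR headset") and adds a queue: "Once instruction is complete, they'll return to the lab waiting area to draw a ticket to provide a specimen IAW standard lab practice".

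The second rating comes at the end: "After undergoing the procedure, each participant will be asked to fill out the post-procedure questionnaire". Its content is described in one sentence: "This questionnaire assesses the patient's pain intensity and level of anxiety with the VAS similar to the VAS shown above". No reference period is given for the anxiety line.

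Section 10.2 lists expected pain and anxiety and then, separately, a pre- and post-procedure anxiety level. It gives no step or time for a second pre-procedure rating.

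On analysis, section 11.1 gives no method for anxiety. Section 11.6 refers to preprocedural anxiety and an average difference that it does not define, and repeats the preprocedural label for the age-group analysis.

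**The concern.** VR is used during the draw, so that is when an effect on anxiety should be largest. As described, the first score is a forecast made at screening. The second is marked when the procedure is over, and participants may read it in two ways: how anxious they were during the draw, or how anxious they are now. If many answer for now, the score describes a time when the stressor has ended, and part of any VR effect may be gone.

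Two conclusions are at risk. A before-to-after fall within the VR arm could be credited to VR, although it would also contain the gap between forecast and experience, the tutorial, any wait and relief at the end. Conversely, a null between-arm result could reflect when and how the question was asked rather than a lack of benefit. A third problem adds to these: if the analysis follows the wording of section 11.6, it uses a score on which VR cannot have acted.

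**Working it through.** **1. The plan's own figure.** The only sample-size figure is for pain (section 11.5): difference 13 mm, SD 17 mm, two-sided alpha 0.05, power 0.80. n per arm = 2 × (1.960 + 0.842)² × (17/13)² = 26.8, so 27. With 10% dropout, 54/0.90 = 60. Both reproduce; an exact t-test calculation gives 27.84, so 28. None of this concerns anxiety, for which the documents give no effect, SD or power. Section 11.6 adds that no minimum clinically significant anxiety score is available.

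**2. The sequence, side by side.**

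| Step | Source | Anxiety rating placed here |
|---|---|---|
| Screening form | 10.1 | Expected anxiety |
| Headset tutorial, 5-10 min, both arms | 10.1, 13.1 | None |
| Envelope | 10.1 (coded number), 13.1 (card stating the arm) | None |
| Waiting area and ticket, length not fixed | 13.1 | None |
| Draw, headset on (VR) or switched off (control) | 10.1 | None |
| Post-procedure form | 10.1 | Level of anxiety, period not stated |

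**3. What each possible comparison can show.** Let P be the screening expectation and Y the post-draw score.
- *Within-arm change, Y − P.* It contains the forecast error, the tutorial, any wait, relief and, in the VR arm, the VR effect. These cannot be separated within one arm.
- *Between-arm difference in Y.* Components with the same mean in both arms cancel: both receive the tutorial, and controls wear a headset that is off. Randomisation keeps this comparison unbiased. What it estimates depends on how participants read the item.
- *Between-arm difference in P.* P precedes allocation in section 10.1, so its expected difference is zero whatever VR does.

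Only the second comparison addresses the anxiety hypothesis directly, and the analysis text does not name it.

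**4. Illustration of lost sensitivity (assumptions only).** Suppose VR lowers anxiety during the draw by 15 mm and a fraction f of the difference remains in the rating. The observed difference is f × 15 mm. Take 30 per arm, a two-sided t-test at 0.05, and an SD of 17 mm (borrowed from the pain calculation) or 25 mm (assumed).

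| f | Observed difference | Power, SD 17 | Power, SD 25 |
|---|---|---|---|
| 1 | 15 mm | 0.92 | 0.63 |
| 0.5 | 7.5 mm | 0.39 | 0.21 |
| 0.2 | 3 mm | 0.10 | 0.07 |

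The table shows how strongly power depends on f. It is not evidence about the value of f; if participants recall the draw, f may be close to 1.

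**The case against.** The strongest reply is that the post-procedure item may already measure anxiety during the draw. It shares a form, a time point and a sentence with the pain item, which is itself recalled. A reader might infer that neither rating captures anxiety during venipuncture. The documents do not support that: the reference period is unstated, and the printed form is not among them. What stands is the ambiguity.

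A reader might also infer that no current pre-procedure rating exists. Section 10.2 leaves one possible; it is simply not placed in the steps.

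Nor does a fall shared by both arms bias the trial. The hypothesis is a contrast between arms, and a shared fall cancels. Whether the post-draw score mostly records relief, or sits near the floor, is not shown anywhere in the documents. It is also not stated when the headset goes on or comes off relative to the needle, so nothing here relies on VR being confined to the moment of puncture.

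Finally, section 9.3 promises only before-and-after ratings for a secondary outcome with no power claim. The missing in-procedure rating is therefore a limit on validity and not a contradiction, and the primary pain outcome is unaffected. All of these replies stand. They leave the undefined post-draw item, the mixed constructs in the pair, and an analysis text that names the wrong score.

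**Conclusion.** The point holds as a weakness in how a secondary outcome is defined and analysed. As written, the pair compares a screening forecast with a rating of unspecified period and cannot be read as a change in one quantity. The between-arm comparison of the post-draw rating is unbiased but may be less sensitive to a VR effect than it could be. The size of that loss cannot be derived from the documents. Separately, the only anxiety score named for analysis is, as section 10.1 places it, rated before allocation and so cannot carry a treatment effect.

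This rests on reading section 10.1 as the complete schedule of ratings. If a further pre-procedure rating is intended under section 10.2, or the printed post-procedure item already refers to the draw, stating so would settle those parts. The gap in the analysis text would remain. The correction is worth making because it costs almost nothing and lets the outcome answer the question asked.

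**What to change.** - Word the post-procedure VAS item as *Level of anxiety during the blood draw*, so that it is tied to the procedure as the pain item is.
- In sections 11.1 and 11.6, name the between-arm comparison of that score as the anxiety analysis, and replace the references to preprocedural anxiety and the undefined average difference.
- Add one 100 mm line, *Level of anxiety right now*, marked after the tutorial and before the envelope is drawn, and use it as the baseline covariate. That position precedes allocation under both descriptions of the envelope. A rating taken later, in the specimen-room chair, would not: under section 13.1 the participant already holds a card stating the arm.
- Keep expected anxiety as a descriptor only, and make section 10.2 list the same ratings as section 10.1.

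Cost: one reworded item and one extra line, under a minute per participant (under an hour in all for 60), with no extra staff. The downside is brief recall, already accepted for pain. The change has to be made before enrolment, because section 16.1 expects data collection to last only 3-4 days and the ratings cannot be recovered afterwards.
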